Title: A randomised crossover trial of five cryocompression devices' ability to reduce skin temperature of the knee.

NCT Number: NCT05355116

Document Date: This version to be uploaded to ClinicalTrials.gov was created on 16th May 2024, though the content below is a carbon copy of the protocol that was approved by the institutional review board on 11th March 2022 prior to the beginning of the study.

Device comparison study protocol (approved by IRB on 11th March 2022)

Introduction

Cryotherapy after surgery is widely utilised and has numerous practical applications for post-operative rehabilitation. Previous research has suggested that during cold therapy, the skin temperature of the knee should be reduced to 10-15°C to maximise the therapeutic benefits of cooling while avoiding the risk of cold injuries such as nerve damage and frostbite (Wilke and Weiner, 2003; Bleakley, McDonough and MacAuley, 2004). However, a recent study noted that where cryocompression devices have previously been used to reduce the skin temperature <10°C, no complications relating to the device have been reported, suggesting that the risk to the user at these lower temperatures is minimal (Bellon *et al.*, 2019). The temperature range at which a cryocompression device should be set in order to achieve a skin temperature within the therapeutic range of 10-15°C is unknown. Furthermore, there is evidence to suggest that the temperature of the device does not equal that to which the skin is reduced (Selfe *et al.*, 2009). Therefore, it is not sufficient to assume that the temperature setting of a cryocompression device accurately reflects skin temperature. Modern cryotherapy devices often consist of some sort of cuff that can be wrapped around the knee, with a connecting tube to a central unit that supplies and circulates ice-water to and from the cuff in order to cool the intended body part. Such devices offer differing levels of control over the temperature of the ice-water as it leaves the central unit, but nothing is known about how this correlates to the skin temperatures that are achieved during a cryotherapy treatment.

The aim of this study is to determine the ability of five different cryocompression devices to effectively lower the skin temperature of the treatment area to within the therapeutic range.

Methods

Design

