This prospective randomised controlled trial will recruit healthy adult volunteers from a university population to participate. To avoid the involvement of individuals with unequal relationships, participants will be recruited through the form of advertisements on staff and student noticeboards, and through an email invitation sent to students within the faculty. A power analysis demonstrated that a total of 30 participants would be required to achieve a power of 0.8 and alpha error probability of 0.05 for a small-medium effect size of $f=0.2$. Each participant will take part in every condition to eliminate the risk of demographic factors confounding the results. Each of the 5 devices being investigated will comprise each of the test conditions. The order in which participants complete the 5 test conditions will be randomised in advance using a computer random number generator. Testing will involve each device being applied and used according to the manufacturers' instructions. Where a device has the ability to apply different temperatures and pressures to participants, settings will be selected in accordance with manufacturer guidelines and recommendations for use. Each testing session will take around 60 minutes to complete, depending on the treatment application guidelines of each device, with at least 24 hours between tests involving the same participant. In total, participants will be giving around 5 hours of time across 5 days to complete their participation.

Inclusion and exclusion criteria

Participants ≥ 18 years old will be considered eligible for the study unless they meet any of the following exclusion criteria, which include the common contraindications for cold therapy (Selfe *et al.*, 2009; Fang *et al.*, 2012; Waterman *et al.*, 2012):

- BMI >40 kg/m²
- History of nerve damage or sensory deficit in the lower limbs (including frostbite)
- Hypersensitivity to cold, including hives
- Active inflammation or pain of the knee
- History of thrombosis, embolism, or other conditions related to impaired peripheral circulation
- Suffering from diagnosed diabetes, multiple sclerosis, rheumatoid arthritis, spinal cord injury, cardiovascular disease, hypertension, Raynaud disease, cryoglobulinemia, or haemoglobinuria
- Confirmed or suspected tissue infection, an unstable fracture, a skin condition, or a tumour in the treatment area
- Cognitive impairment or communication barriers where adjustments can not be reasonably made

Protocol

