Upon completion of a test, the cuff will be removed. If the temperature of the skin has been reduced to within 10-15°C, skin temperature will continue to be monitored every 5 minutes after the cuff has been removed until it rises above 15°C, at which point the test will end. This will allow for the total time to be measured that skin temperature remains within the target therapeutic range as a result of a single application of the cryocompression device. If the skin temperature is not reduced to within 10-15°C while the cuff is worn, then the test will end after the cuff is initially removed. Upon completion of the test, the temperature sensor will be removed from the leg of the participant; thus completing their participation in the test. Once each participant has taken part in all conditions, they will have completed their participation in the study.

The following measures will be recorded: skin temperature at each time point, minimum skin temperature achieved, time to achieve minimum skin temperature, length of time with skin temperature within therapeutic range of 10-15°C. After each test, participants will also be asked to respond to the following question using a 5-point Likert scale: "How comfortable did you find the treatment you just experienced?" The possible answers to this question will be: "Very comfortable, Comfortable, Neutral, Uncomfortable, Very uncomfortable". This will provide insight into differences in perception of the treatment, which could be relevant for the likelihood of protocol adherence by patients in clinical settings.

Analysis

The data will be analysed to detect any differences during testing compared to baseline measures, and between groups. All data will be first subjected to a Kolmogorov-Smirnov test to assess whether they are normally distributed. A repeated measures analysis of variance will be performed on all normally distributed data. A Friedman test will be performed on any data that are not normally distributed.

Ethical issues

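### No primary measure and no rule for comparing devices: if each of the five unranked measures is tested at 0.05, the named overall tests alone carry about a 0.13-0.23 chance of a false difference

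*Combined protocol and SAP*

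**What the plan says.** The Introduction gives the aim as finding out how well five devices can "effectively lower the skin temperature of the treatment area to within the therapeutic range".

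Under Methods, the Design section says that "a total of 30 participants would be required to achieve a power of 0.8" with "alpha error probability of 0.05", "for a small-medium effect size of" f = 0.2. It does not say which measure this calculation is for. Every participant uses all five devices.

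The Protocol section lists the outcomes: "The following measures will be recorded: skin temperature at each time point, minimum skin temperature achieved, time to achieve minimum skin temperature", followed by the length of time in the 10-15°C range. A 5-point comfort rating is taken after each test. That makes four temperature measures plus comfort, and none is called primary.

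The Analysis section sets the scope: "The data will be analysed to detect any differences during testing compared to baseline measures, and between groups". Its tests are a repeated measures analysis of variance for normally distributed data and a Friedman test otherwise. It gives no significance level, order of testing, follow-up comparison of devices or adjustment for multiple tests.

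**The concern.** A significance level of 0.05 describes one test. Here at least five tests are in scope with nothing to rank them, so any of them could carry the conclusion and the lead measure could be chosen after the results are known. The aim does not settle the matter. Minimum temperature, time in range and temperature at each time point could each answer it, and they can rank devices differently: a device that takes the skin below 10°C does well on minimum temperature but may lose time in range.

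The named tests also stop short of the question. Analysis of variance and the Friedman test can show that some device differs, but not which one. A statement about a particular device needs comparisons between devices, and the plan does not say how these will be made or how their error will be limited. At stake is whether a reported difference between named commercial devices can be read at the strength that a 0.05 level suggests.

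**Working it through.** **Inputs from the document.** N = 30, five devices, f = 0.2, alpha 0.05, power 0.8 (Design); four temperature measures plus comfort (Protocol). Five devices give 5 × 4 / 2 = 10 pairs.

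**Assumptions, because the document is silent.** Each test is run at 0.05. Correlation between devices within a participant is 0.5, sphericity holds (epsilon = 1) and nobody drops out. Correlation between measures ranges from 0 to 0.8. Simulated data are normal.

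**1. The plan's own figure.** For a one-group repeated measures analysis of variance with m = 5 conditions, the noncentrality is λ = f² × N × m / (1 − ρ), with m − 1 and (N − 1)(m − 1) degrees of freedom. At N = 30 and ρ = 0.5:

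λ = 0.04 × 30 × 5 / 0.5 = 12, with 4 and 116 degrees of freedom, giving power 0.784.

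Power first reaches 0.8 at N = 32. The stated 30 is therefore close to what one overall test on one measure needs at ρ = 0.5. Other correlations do not fit: N = 38 at ρ = 0.4 and N = 26 at ρ = 0.6. So the calculation is consistent with a single measure, but the plan does not say which.

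**2. The tests the plan names.** If all devices are equal and the measures are independent, the chance of at least one false positive in five tests is 1 − 0.95⁵ = 0.226. Simulation (10,000 replicates, N = 30) gave:

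| Correlation between measures | Any of five overall tests | Pairs tested only after a significant overall test | Ten pairs on all five measures, unadjusted and ungated |
|---|---|---|---|
| 0 | 0.217 | 0.217 | 0.82 |
| 0.3 | 0.215 | 0.215 | 0.78 |
| 0.5 | 0.188 | 0.188 | 0.74 |
| 0.8 | 0.133 | 0.133 | 0.58 |

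The first result column is the plan as written. With the exact independent value as its upper end, the range is 0.13-0.23. The last column is a worst case that the plan does not describe; allowing for simulation error, it is 0.58-0.83. On one measure alone, ten unadjusted pairs give about 0.29.

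**3. When devices are not all equal.** Suppose one device truly differs and the other four are the same. Those four form 4 × 3 / 2 = 6 null pairs. Tested at 0.05 without adjustment on one measure, they give at least one false positive with probability 0.208 (20,000 replicates). Requiring a significant overall test first gives little protection here, because the real difference can make that test significant.

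**4. What control would cost.** Take device means (−x, 0, 0, 0, x). Then f² = 2x²/5, so x = 0.2 × √2.5 = 0.316 SD. One pair differs by 2x = 0.632 SD, six pairs differ by 0.316 SD and three do not differ. At ρ = 0.5 the SD of a paired difference is √(2 × 0.5) = 1, so the noncentrality of the paired t-test is the difference × √30:

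- 0.632 × √30 = 3.46: power 0.92 at 0.05, and 0.66 at 0.005.
- 0.316 × √30 = 1.73: power 0.39 at 0.05, and 0.12 at 0.005.

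The 0.005 is 0.05 / 10, the strictest Holm step.

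**The case against.** Four objections have force.

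- **The 0.05 is only an input to the power calculation.** The plan never presents it as the trial's overall chance of a false device claim. This stands. A reader might infer that the plan asserts a trial-wide rate and gets it wrong, but the text makes no such assertion. The error rates here rest on the assumption that each test would be run at 0.05.
- **Pairwise tests are not planned.** This also stands: they are left open, not specified. A reader might infer that a false device claim is likely even if all devices are equal. That needs all 50 pairwise tests, unadjusted and run whatever the overall tests show, and the document contains no such procedure. For the named tests the figure is 0.13-0.23, and testing pairs only after a significant overall test leaves it at 0.13-0.22.
- **Equality of all devices is a poor model.** The Protocol section says that settings vary between devices, so some real differences are plausible. That is why the case of one differing device is worked above. It does not remove the problem: about 0.21 remains on a single measure.
- **Comfort reads as supportive.** The Protocol section introduces it as insight into how the treatment is perceived. But the Analysis section does not set it apart from the other measures. Dropping it leaves four tests, and 1 − 0.95⁴ = 0.185 if independent.

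The lack of a primary measure, a follow-up procedure and an adjustment is not answered by any of these.

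**Conclusion.** The concern holds as a weakness in the planned analysis that should be corrected. Tested at 0.05 each, the five overall tests carry about a 0.13-0.23 chance of at least one false difference when all devices are equal, roughly three to four and a half times 0.05, and they cannot identify the device. The device-level comparisons that the aim needs have no stated error control: about 0.21 on one measure if one device differs, with 0.58-0.83 only as an ungated worst case.

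The range rests on correlations between measures that the document does not give, on normal data and on five tests. Five is a low count, since temperature is read at seven or more time points and compared with baseline as well. The documents do not support saying that the plan misstates its overall error rate, or that a false claim is more likely than not under the tests it names.

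**What to change.** Before the data are seen:

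1. Name one primary measure that matches the aim, and state that the 0.05 and the 0.8 apply to it. Time within 10-15°C is one option, but it is read on a 5-minute grid and can be zero, so f = 0.2 would need its own justification for that measure. Minimum skin temperature is another option.
2. Test devices overall on that measure, then report all ten pairs with Holm-adjusted p-values and confidence intervals.
3. Label the other temperature measures and comfort as secondary, and report them as estimates with intervals.

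If the data have already been examined, the choice of measure is post hoc and should be reported as such.

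The change needs wording and no more participants if f = 0.2 can be defended for the chosen measure. The cost is pairwise power. In the pattern worked above, the most separated pair falls from 0.92 to 0.66 at the strictest Holm step, and the six pairs differing by 0.32 SD fall from 0.39 to about 0.12. Later Holm steps are less strict, so these are the lower figures. Keeping all five measures on equal terms would cost more: with Bonferroni at 0.05 / 5 = 0.01, the power of each overall test at N = 30 falls from 0.784 to 0.562, and 44 participants would be needed for 0.8.

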All eligible participants will first be required to provide informed consent prior to their participation in the study. Once this has been obtained, participants will each attend 5 individual testing sessions, each lasting no longer than 60 minutes. The height and mass of the participants will be measured during the first testing session in order to calculate BMI, and participants' age and sex will be recorded and included in the later data analysis.

Participants will be required to remain in a seated position with their leg in full extension and elevated, parallel to the floor, for the duration of each test. The leg that will be used for the study will be randomly selected for each participant, and will remain the same for each condition. Skin temperature will be measured using a thermocouple, which will be attached with tape 20 mm distal to the patella. One of the cryocompression devices (Physiolab S1; Physiolab ice pack; GameReady; Cryo/Cuff; or VPulse) will then be attached to the leg of the participant and the test will begin. Depending on the condition to which a participant has been randomly assigned for a given test, a different device will be used. The temperature and pressure settings for each test will be set according to the manufacturers' recommendations which vary between devices. The lowest temperature setting that will be used throughout the study will be 1°C (GameReady device) and the highest pressure setting that will be used is 50 mmHg (GameReady and Physiolab S1 devices). None of the temperature or pressure settings used are deemed to be unsafe or have a high risk of adverse reactions, as long as participants are not contraindicated according to the abovementioned exclusion criteria.

The temperature of the skin will be measured using a k-type thermocouple attached to an infrared thermometer immediately prior to the application of a device, and then every 5 minutes for the duration of the test. The length of a test will be 30 minutes, in accordance with the manufacturers' instructions/recommendations for each device.

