There is a low risk of cold injury to participants if their skin temperature is reduced to <10°C for any prolonged period of time (>60 mins). The coldest temperature setting for this study is 1°C (GameReady), which will be applied for 30 mins. A recent study conducted at the University of Winchester demonstrated that device temperature settings do not equal the actual skin temperatures achieved, and it is not expected that skin temperatures will be reduced to lower than 6°C for more than 15 minutes during any test. Therefore, the risk of harm to the participant is deemed to be minimal for this study.

Participants have the right to withdraw themselves and any collected data from the study at any time during, and for the first 7 days after, their participation without having to give a reason. They also have the right to terminate a test session at any time. Testing shall also be terminated as a result of any adverse reactions that emerge. Adverse reactions (e.g. pain) to the testing protocol are not expected due to the low-risk nature of the study, however any that occur shall be recorded and monitored until things return to baseline/normal. In

order to monitor any pain/discomfort that might occur, a Numerical Pain Rating Scale (0-10 scale) will be within sight of the participant at all times during testing: a test will be terminated if reported pain/discomfort exceeds 5/10, though none is expected. Any reported pain (or other adverse reactions) shall be stored along with the data collected for that participant. If a test is terminated for a reason that could be mitigated in future, participants will be offered the opportunity to repeat the test another day, should they wish to continue taking part in the study. If a test is terminated due to an adverse reaction that can not be mitigated in future, the participant (and any collected data) will be thanked for their time and withdrawn from the study.

Conflict of interest declaration

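### The aim is whether each device brings skin to within 10-15°C, but the Analysis plans only tests of difference, with no per-device estimate of attainment and no rule for tests that go below 10°C

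*Combined protocol and SAP*

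**What the plan says.** The Introduction states the aim as "to determine the ability of five different cryocompression devices to effectively lower the skin temperature of the treatment area to within the therapeutic range", and gives that range as 10-15°C.

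Under Protocol, skin temperature is read "immediately prior to the application of a device, and then every 5 minutes for the duration of the test", with a 30-minute test. The listed measures are temperature at each time point, minimum temperature, time to the minimum, and "length of time with skin temperature within therapeutic range of 10-15°C".

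The Analysis section is one short paragraph: "The data will be analysed to detect any differences during testing compared to baseline measures, and between groups". It then gives a normality check, followed by repeated measures ANOVA or a Friedman test. It plans no proportion, no per-device estimate, no confidence interval and no comparison with 10 or 15°C.

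On temperatures below 10°C, the Introduction first ties the range to avoiding cold injury. It then says of earlier device use that "no complications relating to the device have been reported, suggesting that the risk to the user at these lower temperatures is minimal". Ethical issues says that "it is not expected that skin temperatures will be reduced to lower than 6°C for more than 15 minutes during any test".

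Two Protocol sentences govern monitoring after the cuff comes off: "If the temperature of the skin has been reduced to within 10-15°C, skin temperature will continue to be monitored every 5 minutes" and "If the skin temperature is not reduced to within 10-15°C while the cuff is worn, then the test will end".

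**The concern.** The aim is a question about each device against a fixed range. The planned tests ask whether readings differ from baseline and whether devices differ from each other. If the plan is followed as written, the report could show that devices cool the skin, and cool it by different amounts, without a pre-stated answer on which of them reach 10-15°C.

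An answer can be worked out later from the readings. But how a test below 10°C counts would then be decided with the data in view. The Introduction gives grounds for either choice, and for a cold device the choice could change the conclusion.

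**Working it through.** **1. The plan's own figure.** Design gives N = 30 for power 0.8, alpha 0.05 and f = 0.2. The within-participant correlation and sphericity factor are not stated; I assume 0.5 and 1. With m = 5 devices, λ = f²·N·m/(1−ρ) = 0.04 × 30 × 5/0.5 = 12, on 4 and 116 degrees of freedom. Power is 0.784, and the smallest N reaching 0.80 is 32. The stated size is thus about right under these assumptions. It is a size for detecting a difference and says nothing about attainment.

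**2. What each planned comparison can show.**

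| Comparison | Shows whether a device reaches 10-15°C? |
|---|---|
| Temperature against baseline | No. Skin can cool significantly and stay above 15°C. |
| Temperature or minimum temperature between devices | No. See step 3. |
| Time in 10-15°C between devices | In part. See step 4. |

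**3. Minimum temperature.** Adding one constant to every value leaves the between-device F and Friedman statistics unchanged. On one simulated set of 30 participants by 5 devices, F = 23.03 and Friedman = 47.65 both before and after adding 7°C. Attainment does change. Assume normal minima with SD 3°C:

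- Device means 10.5 to 14.5°C: P(minimum ≤ 15) is 57-93%; P(10 ≤ minimum ≤ 15) is 50-60%.
- Device means 17.5 to 21.5°C: 1.5-20% on either definition.

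This result is for minimum temperature only.

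**4. Time in range.** This measure does not share that property: moving the temperatures moves the times. If no device reached the range, every time would be 0 and no difference could appear, so a significant difference implies that at least one device reached it. What the test leaves open is which devices, and in what share of tests. Five devices all at 0 minutes and five all at the same long time both give no difference. A device that passes quickly through the range to below 10°C can have the same short time as one that barely enters it.

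**5. The definition below 10°C.** Ethical issues excludes, as an expectation, only more than 15 minutes below 6°C, so readings below 10°C remain possible. The documents give no means or SDs; those here are assumed. With Φ the normal distribution function, strict attainment is Φ((15−μ)/σ) − Φ((10−μ)/σ), and broad attainment is Φ((15−μ)/σ).

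| μ (°C) | σ (°C) | Strict: minimum in 10-15°C | Broad: minimum ≤ 15°C |
|---|---|---|---|
| 8 | 2 | 0.9998 − 0.8413 = 0.158 | 0.9998 |
| 8 | 3 | 0.9902 − 0.7475 = 0.243 | 0.990 |
| 8 | 4 | 0.9599 − 0.6915 = 0.268 | 0.960 |
| 12.5 | 2 | 0.8944 − 0.1056 = 0.789 | 0.894 |

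A third definition, any reading in 10-15°C, lies between the two.

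**6. Precision at n = 30.** Wilson 95% intervals: 3/30 gives 3.5-25.6%, 9/30 gives 16.7-47.9%, 15/30 gives 33.2-66.8%, 21/30 gives 52.1-83.3%, 27/30 gives 74.4-96.5%. Half-widths are about 11-17 points. For mean time in range, the t interval half-width is 0.373 × SD, or 1.9-3.7 minutes for an assumed SD of 5-10 minutes.

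**7. Monitoring after cuff removal.** Skin that starts warmer and ends below 10°C has passed through the range with the cuff on. On that reading the sentence that ends the test does not apply, and monitoring until skin rises above 15°C works from below. Neither sentence names this case, however. With readings every 5 minutes, skin could also cross the range between two readings.

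**The case against.** The strongest reply is that time in 10-15°C is already a listed measure and would be tested between devices. Tabulated by device with minimum temperature, it would go a long way towards the aim, and nothing in the Analysis section rules out such tables. The aim also speaks of a device's ability, not of a share of users, so a proportion is one reasonable summary among several. All of this stands. What remains is that no per-device summary is planned and attainment is not defined.

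A reader might infer that every planned test can be significant, or not, whether or not any device reaches the range. The documents do not support that: it is true of temperature and minimum temperature, but not of time in range.

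A reader might also infer that minutes in range will be lost for tests below 10°C at cuff removal. That needs the less natural reading of the monitoring sentences.

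Nor do the documents predict that tests will go below 10°C. The Introduction describes earlier device use, and Ethical issues only leaves the possibility open.

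**Conclusion.** The point holds as a gap between aim and analysis, and the plan should be amended. As written, it gives no pre-stated answer to whether each device reaches 10-15°C, and it does not say how a test below 10°C counts. The first part follows from the text and needs no assumed figures.

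The size of the second part depends on how cold a device runs. Under normal minima it is large at an assumed mean of 8°C (16-27% against 96-99.98%) and modest at 12.5°C with SD 2°C (79% against 89%). These figures show what is possible, not what is likely. The monitoring wording is a minor point. Because temperature at each time point is recorded, cuff-on attainment can still be derived, so the gap is in the analysis plan and not in the cuff-on data.

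**What to change.** Keep the planned tests and add the following.

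1. From the six cuff-on readings of a completed test (5 to 30 minutes, 30/5 = 6), class each test as:
   - A: never at or below 15°C;
   - B: at least one reading in 10-15°C and none below 10°C;
   - C: at least one reading in 10-15°C and at least one below 10°C;
   - D: below 10°C with no reading in 10-15°C.

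   Report each device's proportion in each class with a Wilson 95% CI.
2. Show attainment under all three definitions, so that none is chosen after the data are seen: in range and never below 10°C (B); any reading in range (B + C); any reading at or below 15°C (B + C + D).
3. Report each device's time in 10-15°C with a 95% CI, and minutes below 10°C beside it.
4. State that significance against baseline is not evidence that the range was reached.
5. Reconcile the two monitoring sentences under Protocol so that it is clear which applies to a test below 10°C at cuff removal. This helps only before data are collected; otherwise, report what was done.

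The cost is a few derived variables and a paragraph of analysis text, with no change to sample size, visits or instruments. Post-removal readings might be added for some tests, depending on how item 5 is settled. With half-widths of about 11-17 points, the proportions are for estimation only, but 21 of 30 or more would still put the interval above 50%, and 9 of 30 or fewer below it.

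### The skin temperature read before each session is not used as a covariate when the devices are compared; adding it is a cheap gain in precision, not a correction of an error

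*Combined protocol and SAP*

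**What the plan says.** The Protocol section has skin temperature taken "immediately prior to the application of a device, and then every 5 minutes for the duration of the test". The Design section puts at least 24 hours between a participant's sessions, so each participant contributes five separate starting temperatures, one per device.

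Besides the temperature at each time point, the Protocol section lists three derived measures: "minimum skin temperature achieved, time to achieve minimum skin temperature, length of time with skin temperature within therapeutic range of 10-15°C".

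The Analysis section states its aim as follows: "The data will be analysed to detect any differences during testing compared to baseline measures, and between groups". For the method it says "A repeated measures analysis of variance will be performed on all normally distributed data" and "A Friedman test will be performed on any data that are not normally distributed". It names no covariate. The Protocol section says that age and sex will enter the later analysis. Both are constant within a participant, so they cannot account for a different starting temperature from one session to the next.

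On order, the Design section says: "The order in which participants complete the 5 test conditions will be randomised in advance using a computer random number generator".

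**The concern.** A crossover removes stable differences between people. It does not remove differences between one person's sessions, and starting skin temperature is such a difference. If a warmer start goes with a warmer minimum, that variation stays in the error term of the device comparison although the reading that explains it has been recorded.

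For minimum temperature, time to minimum and time within 10-15°C, each a single value per session, the plan states no use of baseline. For the serial readings the wording is open: it could mean raw values, change from baseline or a device-by-time model. What is at stake is the width of the confidence intervals for device differences and the power of the overall test.

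**Working it through.** **Inputs from the document (Design section).** N = 30 participants, m = 5 conditions, alpha = 0.05, f = 0.2, target power 0.8.

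**Assumptions, not in the document.** rho, the correlation between a participant's outcomes under different devices, is set to 0.5. Sphericity holds (epsilon = 1). r, the within-person correlation between session baseline and outcome, is shown over a range.

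**Step 1: the plan's own figure.** The plan says "A power analysis demonstrated that a total of 30 participants would be required to achieve a power of 0.8". For a one-group repeated measures ANOVA:

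lambda = N × m × f² / (1 − rho) = 30 × 5 × 0.04 / 0.5 = 12.0, with df = 4 and 4 × 29 = 116.

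The noncentral F gives power 0.784 at N = 30, and 80% power needs N = 32. The stated 30 is therefore reproduced closely, though not exactly, at rho = 0.5.

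**Step 2: add the session baseline.** The residual within-person variance is multiplied by (1 − r²) and one error df is lost (115):

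lambda = 12.0 / (1 − r²).

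| r | lambda | power | standard error ratio, √(1 − r²) |
|---|---|---|---|
| 0 | 12.00 | 0.784 | 1.000 |
| 0.1 | 12.12 | 0.788 | 0.995 |
| 0.2 | 12.50 | 0.802 | 0.980 |
| 0.3 | 13.19 | 0.826 | 0.954 |
| 0.5 | 16.00 | 0.899 | 0.866 |

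To four places, power at r = 0 goes from 0.7839 to 0.7837.

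**Step 3: check by simulation.** With normal outcomes and 20,000 runs per setting, power without/with baseline was 0.783/0.779 (r = 0), 0.784/0.786 (0.1), 0.784/0.797 (0.2), 0.780/0.820 (0.3) and 0.789/0.899 (0.5). So the change is about −0.4 percentage points at r = 0, negligible at 0.1, about +1 at 0.2, +4 at 0.3 and +11 at 0.5. Type I error with baseline was 0.049 to 0.052 (10,000 runs).

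**Step 4: sensitivity to the other assumptions, at r = 0.3, by formula.** rho = 0.4: 0.696 to 0.742. rho = 0.6: 0.877 to 0.908. epsilon = 0.75: 0.690 to 0.735. The gain stays at 3 to 5 points.

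**Step 5: can the gain be tied to the 0.8 target?** Unadjusted power reaches 0.80 at rho of about 0.517. At rho = 0.55 it is 0.830 without baseline, while at rho = 0.45 it is still only 0.783 with baseline at r = 0.3. Adjustment takes power from below to above 0.80 only for rho between about 0.497 and 0.517 (r = 0.2) or 0.470 and 0.517 (r = 0.3).

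**The case against.** **The unadjusted analysis is acceptable.** This stands. A reader might infer that leaving out baseline biases the device comparison. It does not: order is randomised and every participant uses every device, so differences in starting temperature between devices arise by chance.

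**Baseline is already used.** This stands in part. The Analysis section names a comparison with baseline, and a device-by-time analysis of the serial readings may be read as comparing change. That does not cover the derived measures, and change is not equivalent to covariate adjustment. With equal baseline and outcome variances assumed, lambda for change scores is 12.0 / (2 − 2r), which gives power 0.453 at r = 0, 0.619 at r = 0.3 and 0.784 at r = 0.5.

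**The benefit may be small.** This stands. It rests on r, which is not given. Minimum temperature and the serial readings are the same quantity at the same site as the baseline, so a positive r is plausible but not shown.

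**Chance imbalance is not a second harm.** This stands. The standard error of a two-device difference is √(2/30) = 0.258 within-person standard deviations. The part carried by baseline, r × 0.258, is the r² share of that same variance and is already in the power figures.

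**Not every outcome suits a single baseline slope.** This stands. The 10-15°C range has two bounds, and the Ethical issues section allows for skin below 10°C. A warmer start could lengthen time in range on a very cold device and shorten it on a milder one. In an illustrative cooling-curve simulation with assumed parameters, the correlation of baseline with time in range ran from +0.29 at a 6°C plateau to −0.43 at a 14°C plateau. The normal-theory figures above do not apply to time in range or time to minimum. Replacing the Friedman test with a rank-based model would be a separate decision.

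**Conclusion.** The point holds as a precision improvement for minimum skin temperature and the serial readings. Under rho = 0.5 and sphericity the gain in power runs from nothing at r = 0 to about 11 points at r = 0.5, and is 1 to 2 points or less for r up to 0.2. Since r is not in the document, the true gain cannot be placed within that range.

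It is tempting to go further and say that, with power at 0.784, the covariate decides whether the trial reaches its target. The document does not support that. It gives no rho, 0.5 is an assumption, and a rho of about 0.517 meets the target without any adjustment. Even at rho = 0.5 and r = 0.2 the two calculations fall on either side of 0.80: 0.802 by formula, 0.797 by simulation.

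**What to change.** **Minimum skin temperature.** Fit a linear mixed model with participant as random effect, device as fixed effect and that session's pre-application temperature as covariate. Enter the covariate as the deviation from the participant's mean of the five baselines, and include that mean as well.

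**Serial readings.** Use the six readings from 5 to 30 minutes as responses, with device, time, device-by-time and the same two baseline terms. Allow for correlation within a session by a session effect with autoregressive residuals, by an unstructured within-session covariance, or by a sphericity-type correction. This matters. With no session effect, simulated type I error of the device test was 0.45, 0.64 and 0.81 at within-session correlations of 0.3, 0.5 and 0.8. With a session intercept alone and autoregressive errors of 0.5, 0.7 and 0.9, the device-by-time test had type I error 0.072, 0.092 and 0.106 (4,000 runs each).

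**Time to minimum and time within 10-15°C.** Keep the planned tests. Any baseline-adjusted version should be a sensitivity analysis only.

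**Cost.** No new data and no change in sample size. One error degree of freedom is lost: if r = 0, that is about 0.0002 in power by formula and about 0.4 percentage points in simulation. The analysis section becomes slightly longer.
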